7.1.4. Need for Rescue Lesional Treatment

Study procedures must be performed before any interventions. Any lesion undergoing an intervention will be documented in the lesion count worksheet (refer to the Study Manual). The site will be required to count any lesion that undergoes an intervention as permanently present from the date of the intervention, and must account for it in the source and on the appropriate eCRF.

7.1.5. Hidradenitis Suppurativa Pain Numeric Rating Scale

The HS Pain NRS will be completed in a daily diary by participants from screening through the follow-up visit (EOS). An 11-point scale will be used to assess the worst skin pain and the average skin pain due to HS based on a recall period of the last 24 hours. Ratings for the 2 items range from 0 (no skin pain) to 10 (skin pain as bad as you can imagine).

7.1.6. Analgesic Use

From Day 1 through the follow-up visit (EOS), participants will complete a daily electronic diary of their analgesic use (yes/no; refer to the Study Manual). All analgesics and dose modifications will be captured in the source and on the appropriate eCRF.

7.1.7. Hidradenitis Suppurativa Patient Global Impression of Change

Participants will complete the HS-PGIC questionnaire at the designated study visits. The HS-PGIC consists of 1 self-administered item that assesses change in the severity of skin in the HS area. Participants are asked to indicate their impression of change compared with their last visit. The participant will answer the following: Since your last visit, your HS is: (1) very much improved, (2) much improved, (3) minimally improved, (4) no change, (5) minimally worse, (6) much worse, or (7) very much worse.

7.1.8. Dermatology Life Quality Index

Participants will complete a DLQI questionnaire from screening through the follow-up visit (EOS). The DLQI will be used to assess the symptoms and the impact of skin problems on quality of life (Hongbo et al 2005). The DLQI can be used to evaluate 6 areas: symptoms and feelings, daily activities, leisure, work and school, personal relationships, and treatment. Participants will be asked to respond to the 10 questions of the DLQI based on a recall period of "the last week." The scoring of each question is as follows:

Very much	Scored 3
A lot	Scored 2
A little	Scored 1
Not at all	Scored 0
Not relevant	Scored 0
Question 7, 'prevented work or studying'	Scored 3

The DLQI is calculated by summing the score of each question resulting in a maximum of 30 and a minimum of 0. The meaning of DLQI scores can be categorized as:

Score	Interpretation
0-1	No effect at all on patient's life
2-5	Small effect on patient's life
6-10	Moderate effect on patient's life
11-20	Very large effect on patient's life
21-30	Extremely large effect on patient's life

[REDACTED]

7.2. Analysis of Efficacy Endpoints

The efficacy endpoints include:

- Proportion of participants with a HiSCR (at least 50% reduction in AN count with no increase in abscess count and no increase in draining fistula count relative to baseline) at each visit;
- Proportion of participants achieving an AN count of 0 to 2 at each visit;
- Mean change from baseline in the HS Pain NRS scores, worst and average pain, at each visit;
- Mean change from baseline to Week 8 in the modified Sartorius scale score;
- Mean change from baseline in the number of draining fistulas count at each visit;
- Proportion of participants at each category of Hurley Stage at baseline and Week 8;
- Proportion of participants with change from baseline in Hurley Stage at Week 8;
- Proportions of participants in each HS-PGIC category during the treatment period;
- Actual measurements in HS-PGIC at each visit;
- Proportion of participants requiring rescue lesional treatment;
- Number of interventions with rescue lesional treatment;
- Proportion of participants at each scoring category of DLQI at each visit;
- Mean change from baseline in DLQI total scores at each visit;

[REDACTED]

Category variables will be summarized using descriptive statistics, including sample size, frequency, and percentages. Continuous variables will be summarized using descriptive statistics, including sample size, mean, median, standard deviation, standard error of the mean, minimum, and maximum.

[REDACTED]

[REDACTED]

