
10.4.2. Efficacy Analyses

Efficacy analyses will be conducted using the FAS. Efficacy assessments will be summarized using descriptive statistics at each visit. The baseline value for a variable will be defined as the last nonmissing value for this variable before or on Day 1, unless otherwise specified.

Categorical variables, including proportions of participants achieving HiSCR, achieving an AN count of 0 to 2, requiring rescue lesional treatment, at each category of Hurley Stage, with a change in Hurley Stage, in each HS-PGIC category, and at each scoring category of DLQI, will be summarized using descriptive statistics, including sample size, frequency, and percentages. Actual measurements of HS-PGIC, mean, change from baseline, and percentage change from baseline in DLQI, HS pain NRS, modified Sartorius scale, and in the number of draining fistulas will be summarized using descriptive statistics, including sample size, mean, median, standard deviation, standard error of the mean, minimum, and maximum. A logistic regression model will be fit for assessment of the dose-response relationship on HiSCR at Week 8.

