2.2. Objectives and Endpoints

[Table 1](#) presents the objectives and endpoints.

Table 1: Objectives and Endpoints

Objectives	Endpoints
Primary	
To determine the safety and tolerability of INCB054707.	
 • Frequency, duration, and severity of AEs, clinical laboratory test results, vital signs results, ECGs, and physical examination findings.
Secondary	
To determine the systemic exposure to INCB054707.	
 • Population PK parameters of INCB054707.
To determine the efficacy of INCB054707.	
 • Proportion of participants achieving a HiSCR at each visit. • Proportion of participants achieving an AN count of 0 to 2 at each visit. • Mean change from baseline in the HS Pain NRS scores, worst and average pain, at each visit. • Mean change from baseline to Week 8 in the modified Sartorius scale score. • Mean change from baseline in the number of draining fistulas count at each visit. • Proportion of participants at each category of Hurley Stage at baseline and Week 8. • Proportion of participants with change from baseline in Hurley Stage at Week 8. • Proportions of participants in each HS-PGIC category during the treatment period. • Actual measurements in HS-PGIC at each visit.
To assess the need for rescue lesional treatment.	
 • Proportion of participants requiring rescue lesional treatment. • Number of interventions with rescue lesional treatment.
To assess patient-reported quality-of-life burden.	
 • Proportion of participants at each scoring category of DLQI at each visit. • Mean change from baseline in DLQI total scores at each visit.

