7. EFFICACY

All efficacy analyses are exploratory. Hence, no p-values will be provided and multiple adjustment will not be made.

[Appendix A](#) provides a list of planned tables, figures, and listings.

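### The visible plan gives no baseline-adjusted estimate for the continuous secondary efficacy endpoints, so part of any chance baseline difference between small groups stays in the mean change and precision is lost

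*SAP*

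**What the plan says.** SAP 7.2 defines the endpoints as changes from baseline. For pain the entry reads "Mean change from baseline in the HS Pain NRS scores, worst and average pain, at each visit". Modified Sartorius follows the same pattern but is limited to the change at Week 8. For DLQI the entry reads "Mean change from baseline in DLQI total scores at each visit". The draining fistula count is treated in the same way. The analysis is one sentence: "Continuous variables will be summarized using descriptive statistics, including sample size, mean, median, standard deviation, standard error of the mean, minimum, and maximum". Redacted blocks follow it.

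Protocol 10.4.2 plans descriptive summaries of "mean, change from baseline, and percentage change from baseline in DLQI, HS pain NRS, modified Sartorius scale, and in the number of draining fistulas". The only efficacy model it names is for a binary endpoint: "A logistic regression model will be fit for assessment of the dose-response relationship on HiSCR at Week 8". SAP Appendix A lists only summary tables for the continuous endpoints.

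The setting is exploratory. SAP 7 states: "All efficacy analyses are exploratory. Hence, no p-values will be provided and multiple adjustment will not be made". Protocol 10.3 calls this a safety study without formal efficacy hypotheses. SAP 3.2 sets 95% as the default confidence level.

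Each cohort has 9 active and 3 placebo participants (SAP 3.1). Results are shown by assigned dose regimen (SAP 5.2). No stratification is described in Protocol 6.3 or SAP 3.1.

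**The concern.** Groups are small and eligibility leaves baselines wide. Protocol 5.1 asks for an abscess and nodule count of at least 3 and Hurley Stage II or III in one area, but sets no minimum pain or DLQI score. Sizeable baseline gaps between groups are therefore likely.

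Change from baseline is negatively correlated with baseline whenever rho is below 1 and the SDs are similar. A group that starts worse by chance tends to show a larger mean improvement, whatever the treatment does. Percentage change does not remove this dependence.

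Protocol 2.2.1 expects the results to inform a larger dose-ranging Phase 2b study. Because no p-values are given, readers will compare point estimates across groups. The baseline values that would sharpen those estimates are already to be collected, and the visible analysis does not use them as a covariate.

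**Working it through.** **Inputs from the documents.** 9 per dose, 3 placebo per cohort, 3 cohorts (SAP 3.1). Pooled placebo would be 3 x 3 = 9, but the visible text does not state pooling.

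**Assumed inputs.** The documents give no rho and no SDs. I take rho = 0.3, 0.5 and 0.7, with 0.9 as an extreme. I assume equal SDs at baseline and follow-up and work in units of that SD.

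**The plan's own figure.** SAP 3.3 claims more than an 85% chance of seeing at least one event at a 20% rate with 9 participants: 1 - 0.8^9 = 0.866. It reproduces. It sets the group size on safety grounds and says nothing about efficacy precision.

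**Step 1: size of chance baseline gaps.** SD of the difference = sqrt(1/n1 + 1/n2).
- 9 v 9: sqrt(2/9) = 0.471. The gap exceeds 0.5 SD in 29% of trials.
- 9 v 3 (one cohort): sqrt(1/9 + 1/3) = 0.667. The gap exceeds 0.5 SD in 45% of trials.

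**Step 2: how much reaches the mean change.** The share is 1 - rho, with sign opposite to the gap. For a 0.5 SD gap, the difference in mean change shifts by 0.35, 0.25 or 0.15 SD at rho 0.3, 0.5 or 0.7. Such gaps account for (1 - rho)/2 = 35%, 25% or 15% of the sampling variance of that difference.

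**Step 3: precision, 9 v 9.**
- SE(change) = 0.471 x sqrt(2(1 - rho)).
- SE(adjusted) = 0.471 x sqrt(1 - rho^2) x sqrt(1 + 1/30). The last factor pays for estimating the slope from 36 participants in 4 groups (36 - 4 - 2 = 30).

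| rho | SE, change | SE, adjusted | SE reduction |
|---|---|---|---|
| 0.3 | 0.558 | 0.457 | 18% |
| 0.5 | 0.471 | 0.415 | 12% |
| 0.7 | 0.365 | 0.342 | 6% |
| 0.9 | 0.211 | 0.209 | 1% |

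The ratio of the two SEs is sqrt((1 + rho)/2 x (1 + 1/30)). At rho 0.9 this is sqrt(0.95 x 1.033) = 0.99.

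**Step 4: simulation check.** With 20,000 trials of 4 groups of 9 under bivariate normality, the variance ratio (adjusted to change) was 0.68, 0.77 and 0.88 at rho 0.3, 0.5 and 0.7. A separate 8,000-run simulation gave SE ratios of 0.822, 0.884 and 0.929, hence 6-7% at rho 0.7.

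**The case against.** The strongest reply is that nothing planned is wrong. Efficacy is exploratory and the sample size rests on adverse-event detection. The visible text specifies no between-group contrast for these endpoints, and descriptive tables are ordinary in an escalation study with 9 per dose. This stands in part: the point asks for an added estimate and does not correct a faulty inference. It does not make the addition pointless, given the Phase 2b aim.

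Other points that stand:

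- **Redaction.** SAP 10.1 declares no change from the protocol's analyses, yet the protocol's HiSCR logistic model is absent from the visible SAP. Modelling text may therefore lie in the redacted blocks. A reader might infer that the SAP certainly has no adjusted analysis, but the documents cannot show that. Protocol 10.4.2, however, names no model for a continuous endpoint.
- **Raw change is not the only summary.** Scores and percentage change are also planned, and Appendix A tables run from baseline, so an imbalance should be visible to readers. None of these summaries adjusts for it.
- **Design.** A placebo group of 9 needs pooling. Cohorts open in sequence (Protocol 6.5.2), so doses are not randomised against one another. Baseline adjustment does not cure that, and adjusted differences with CIs could lend such comparisons undue authority.
- **Size.** Modified Sartorius counts scars and non-draining fistulas (SAP 7.1.3). Protocol 2.1.2 says scarring and fistulas are not expected to respond to drugs. A high rho over 8 weeks, and hence almost no gain, is plausible there.
- **Model fit.** Pain (0-10) and DLQI (0-30) are bounded, and Sartorius is built from counts. An extreme baseline can pull the slope.

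**Conclusion.** The point holds in a limited form. The visible plan has no baseline-adjusted estimate for pain, modified Sartorius, DLQI or draining fistula count. Using the baselines already collected would reduce the SE of a dose-placebo difference by about 18%, 12% or 6-7% at rho 0.3, 0.5 or 0.7, and by about 1% at 0.9. These figures assume equal SDs, normality, a linear baseline effect and placebo pooled to 9. Rho is an assumption throughout.

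Two stronger readings are not supported. A reader might infer that baseline imbalance passes in full into the results. It does not, because change subtracts baseline and only 1 - rho remains. A reader might also infer that the results are biased or a test is invalid. For a dose against its own cohort's randomised placebo, imbalance is chance error, and no test of these endpoints is planned. Differences between sequential cohorts are a separate matter that this adjustment does not resolve.

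**What to change.** 1. Keep the descriptive tables. Add to SAP 7.2 a supportive linear model for change at each post-baseline visit where the endpoint is analysed (Week 8 for modified Sartorius), with treatment group and the participant's own baseline as terms.
2. State that placebo is pooled across cohorts. Report adjusted means and dose-placebo differences with 95% CIs and no p-values, beside baseline means by group.
3. Add a note that doses come from sequential cohorts not randomised against each other, and that baseline adjustment does not remove cohort differences.
4. Reconcile the pain baseline before fitting the pain model. Protocol 8.2.5 starts the bedtime diary on Day 1, while SAP 7.1.5 starts it at screening. Protocol 10.4.2 allows a Day 1 value as baseline, while SAP 4.1.3 requires one from before the first dose. Under the SAP's definition, a diary begun on Day 1 and filled in at bedtime, after dosing at the site that day, supplies no baseline.

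The cost is SAP wording, one extra table per endpoint, one degree of freedom, and a linearity assumption on bounded or skewed scores. No new data are needed beyond a settled pain baseline. If the redacted text already contains such a model, only items 2 to 4 need checking.

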8. SAFETY AND TOLERABILITY

[Appendix A](#) provides a list of planned tables, figures, and listings.

8.1. General Considerations

Summary tables may be replaced with listings when appropriate. For instance, an AE frequency table may be replaced with a listing if it only contains a few unique preferred terms reported on relatively few participants.

Unless otherwise stated, table summaries will be limited to AEs occurring within 30 days of the last administration of study drug.

8.2. Adverse Events

8.2.1. Adverse Event Definitions

A TEAE is any AE either reported for the first time or worsening of a pre-existing event after first administration of study drug. Analysis of AEs (as discussed below) will be limited to TEAEs, but data listings will include all AEs regardless of their timing in relation to study drug administration.

Adverse events will be tabulated by MedDRA PT and SOC. Severity of AEs will be graded using the NCI CTCAE. The CTCAE v4.03 is used for this study. The CTCAE reporting guidelines and grading details are available on the Cancer Therapy Evaluation Program website.

The subset of AEs considered by the investigator to be related to study drug will be considered to be treatment-related AEs. The incidence of AEs and treatment-related AEs will be tabulated. Serious TEAEs will also be tabulated.

Any missing onset date, causality, or severity must be queried for resolution. Unresolved missing causality and severity will be handled according to the following rules:

- An unresolved missing causality will be considered treatment-related.
- An unresolved missing severity will be identified as an unknown severity.

For purposes of analysis, all AEs will be considered TEAEs unless the AE can unequivocally be defined as not treatment-emergent.

8.2.2. Adverse Event Summaries

An overall summary of AEs will include:

- Number (%) of participants reporting any TEAEs
- Number (%) of participants reporting any serious TEAEs
- Number (%) of participants reporting any Grade 3 or higher TEAEs
- Number (%) of participants reporting any treatment-related TEAEs
- Number (%) of participants who temporarily interrupted study treatment because of TEAEs

- Number (%) of participants who permanently discontinued study treatment because of TEAEs
- Number (%) of participants who had a TEAE leading to death

The following summaries will be produced by MedDRA term (if 2 or fewer participants appear in a table, a listing may be appropriate):

- Summary of TEAEs by SOC and PT
- Summary of TEAEs by PT in decreasing order of frequency
- Summary of TEAEs by SOC, PT, and maximum severity
- Summary of treatment-related TEAEs by SOC and PT
- Summary of treatment-related TEAEs by PT in decreasing order of frequency
- Summary of treatment-related TEAEs by SOC, PT, and maximum severity
- Summary of Grade 3 or higher TEAEs by SOC and PT
- Summary of Grade 3 or higher treatment-related TEAEs by PT
- Summary of Grade 3 or higher TEAE by PT in decreasing order of frequency
- Summary of TEAEs leading to death by SOC and PT
- Summary of serious TEAEs by SOC and PT
- Summary of serious TEAEs by PT in descending order of frequency
- Summary of serious treatment-related TEAEs by SOC and PT
- Summary of TEAEs leading to dose interruption by SOC and PT
- Summary of TEAEs leading to discontinuation of treatment by SOC and PT
- Summary of nonserious TEAEs by SOC and PT

8.3. Clinical Laboratory Tests

8.3.1. Laboratory Value Definitions

All laboratory assessments (refer to Protocol Table 11) will be performed using a central laboratory except for urine pregnancy tests (as applicable) or tests that are deemed necessary by the investigator for participant management (refer to Protocol Section 8.3.5). Laboratory values, change from baseline values, and percent change from baseline values will be summarized descriptively by visit. Baseline values will be determined using the nonmissing values collected before the first administration, prioritizing scheduled assessments over unscheduled visits. For baseline laboratory candidates with the same date and time in the same priority category, additional rules may be provided after consultation with the medical monitor to delineate which value will be defined as baseline.

8.3.2. Laboratory Value Summaries

Clinical laboratory tests, including hematology, serum chemistry, urinalysis, lipid panel, serology, C-reactive protein, follicle-stimulating hormone, serum pregnancy test, urine pregnancy test, and QuantiFERON-TB Gold test (refer to Protocol Table 11), will be performed for each participant during the study in accordance with study schedule of assessments (refer to Protocol Table 3). If specific safety issues arise, additional unscheduled laboratory tests/analyses may be performed at the discretion of the investigator.

All test results and associated normal ranges from central laboratories will be reported in SI units. All tests with numeric values will have a unique unit per test. Any laboratory test results and associated normal ranges from local laboratories will be converted to SI units. For the limited number of cases where the associated normal ranges from a local laboratory cannot be obtained despite due diligence, associated central laboratory normal ranges will be applied. In the event that central laboratory normal ranges are not available, a set of standard normal ranges based upon documented reference ranges will be applied to facilitate reporting the test results.

When there are multiple laboratory nonmissing values for a participant's particular test within a visit window, the smallest laboratory sequence number will be used to identify the record for postbaseline visits.

Laboratory parameters identified in Protocol Table 11 will be summarized. Shift tables based on worst postbaseline value recorded will use all postbaseline values occurring within 30 days of stopping study treatment. Other laboratory parameters collected will only be listed in an appendix to the CSR in their original units without SI conversions.

Actual values and changes from baseline in clinical laboratory test results will be summarized using descriptive statistics. Laboratory test values outside the normal range will be assessed for severity based on the normal ranges for the clinical reference laboratory. The incidence of abnormal laboratory values will be tabulated.

Laboratory data will be classified into Grades 1 through 5 using CTCAE v4.03. The following summaries will be produced for the laboratory data:

- Number and percentage of participants with worst postbaseline CTCAE grade (regardless of baseline value). Each participant will be counted only for the worst grade observed postbaseline.
- Shift tables from baseline to the worst postbaseline value using CTCAE grade. The denominator for the percentage calculation will use the number of participants in the baseline category (ie, low, high, normal, missing) as the denominator for the percentage in each of the categories during the treatment period.
- For laboratory parameters where CTCAE grades are not defined, shift tables to the worst postbaseline value using the low/normal/high classifications based on laboratory reference ranges.

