Optional photography (target area)	8.2.9		X			X		X	

^a An overnight (at least 8-hour) fast will be required at these visits. Participant will take study drug at the study sites.

^b Participants will take study drug before the study visit.

^c For confirmation of nonchildbearing status for women who are postmenopausal, defined as amenorrhea at least 12 months before screening.

^d For women of childbearing potential only. Serum test will be conducted at screening and urine test will be conducted at all other visits.

^e A brief neurological examination will also be performed.

^f If there is a potential clinically significant abnormality in chemistry or hematology assessments (particularly in platelet count) at Week 2, 4, or 6, then an unscheduled visit the following week (Weeks 3, 5, 7) to repeat the assessment is required.

^g See [Table 10](#).

^h The HS Pain NRS includes worst pain and average pain in the last 24 hours.

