8.6. Unscheduled Visits

Unscheduled visits may occur at any time at the investigator's discretion, and appropriate clinical and laboratory tests may be performed, as clinically indicated.

If there is a potential clinically significant abnormality in hematology or chemistry assessments (particularly in platelet count) at Weeks 2, 4 or 6, an unscheduled visit the following week (Weeks 3, 5, 7) to repeat hematology assessments is required (see Section 8.3.5.1). See Section 6.5 for the instruction of dose interruption and restart. The investigator must inform and consult sponsor with any hematological abnormality.

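### SAP 8.3.2 picks postbaseline by-visit laboratory values by sequence number with no priority for the scheduled sample, so under some visit windows an unscheduled sample can replace it

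*SAP*

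**What the plan says.** Where a participant has more than one usable result for the same test around one visit, SAP 8.3.2 rules that "the smallest laboratory sequence number will be used to identify the record for postbaseline visits". The rule does not mention whether a sample was scheduled, how far it lies from the nominal day, or whether it was valid. The available SAP text defines neither the laboratory visit window nor the sequence number.

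The rule feeds the by-visit output promised in SAP 8.3.1: "Laboratory values, change from baseline values, and percent change from baseline values will be summarized descriptively by visit". In Appendix A these are Tables 3.3.1 (hematology) and 3.3.4 (chemistry).

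Elsewhere the SAP favors scheduled data. Laboratory baseline is chosen by "prioritizing scheduled assessments over unscheduled visits" (SAP 8.3.1). SAP 4.1.3 prefers the scheduled assessment for same-day ties at baseline, and SAP 8.4 summarizes vital signs at scheduled visits.

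Extra samples are expected. If hematology or chemistry at Week 2, 4 or 6 shows a possibly important abnormality, platelets above all, "then an unscheduled visit the following week (Weeks 3, 5, 7) to repeat the assessment is required" (Protocol Table 3, footnote f). In addition, "Unscheduled visits may occur at any time at the investigator's discretion" (Protocol 8.6), and "If specific safety issues arise, additional unscheduled laboratory tests/analyses may be performed at the discretion of the investigator" (SAP 8.3.2).

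The shift tables to the worst value are handled separately: they "will use all postbaseline values occurring within 30 days of stopping study treatment" (SAP 8.3.2).

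**The concern.** A by-visit table should describe each participant at about the same time on treatment. If the retained record is simply the lowest-numbered one, an unscheduled sample can stand in for the scheduled sample, and the visit label no longer describes when the blood was drawn. The plan guards against this at baseline but not afterwards, and gives no reason for the difference.

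The required repeats, and the extra tests that SAP 8.3.2 ties to safety issues, arise from possible safety findings. Any substitution from these sources would therefore fall on the participants of most interest. Protocol Table 8 also allows treatment to be interrupted for up to 14 days for low blood counts, so a Week 3 sample reported as Week 4 could come from a different dosing state. Protocol 2.2.1 justifies the 8-week treatment period partly by the evaluation of hematologic effects. With about 9 participants per dose, one or two substitutions can move a visit mean.

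**Working it through.** The plan attaches no figure to this rule. Its one computable design figure, a greater than 85% chance of seeing at least one event among 9 participants at a 20% rate (SAP 3.3), reproduces as 1 − 0.8^9 = 0.866. The point does not depend on it; only the 9 per dose is used below.

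**Inputs.** Visit tolerance is ±3 days at Weeks 2, 4, 6 and 8 (Protocol Table 3). Repeats are due the week after an abnormal Week 2, 4 or 6 result. Day 1 is the first dose (SAP 4.1.1), so Week w falls on Day 7w + 1. Assumptions: sequence numbers follow collection order, and a required repeat comes exactly 7 days after the actual visit.

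**When displacement happens.** The unscheduled sample must lie in the same window as a scheduled sample and come before it. A repeat taken after the scheduled sample in the same window has the larger number, so the scheduled value is kept.

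**Case A: windows equal to the ±3-day tolerance.**

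| Visit | Nominal day | Window (days) | Repeat 7 days later (days) | Next window (days) |
|---|---|---|---|---|
| Week 2 | 15 | 12–18 | 19–25 | 26–32 |
| Week 4 | 29 | 26–32 | 33–39 | 40–46 |
| Week 6 | 43 | 40–46 | 47–53 | 54–60 |

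A 7-day repeat falls in no window. To reach the Week 4 window, a repeat of a Week 2 test done on Day d needs a gap of at least 26 − d days: 14 for Day 12, 11 for Day 15, 8 for Day 18. The same gaps apply after Weeks 4 and 6. Otherwise displacement needs a discretionary early check, such as an unscheduled sample on Day 27 before a scheduled Week 4 sample on Day 30.

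**Case B: contiguous windows split at the midpoint.** The midpoint of Days 15 and 29 is Day 22. A repeat on Day d + 7 enters the Week 4 window as follows:

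- If Day 22 belongs to Week 4: d + 7 ≥ 22, so d = 15, 16, 17 or 18, which is 4 of the 7 allowed visit days.
- If Day 22 belongs to Week 2: d + 7 ≥ 23, so d = 16, 17 or 18, which is 3 of 7.

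The counts are the same around Days 36 and 50. In each of these cases the repeat precedes the next scheduled sample and replaces it. For a visit exactly on target, the outcome depends entirely on which window takes the midpoint. These are counts of allowed days, not probabilities.

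**Size of a shift.** If k of 9 participants have their value replaced, each differing by D in the same direction, the visit mean moves by k × D / 9. The values of k and D are assumed; the documents give neither.

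| k | D = 25 | D = 50 | D = 100 |
|---|---|---|---|
| 1 | 2.8 | 5.6 | 11.1 |
| 2 | 5.6 | 11.1 | 22.2 |
| 3 | 8.3 | 16.7 | 33.3 |

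All entries are platelets, ×10^9/L.

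**The case against.** The case for leaving the rule alone has four parts.

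- **The required repeats seldom meet the rule.** The only windows in the documents are the Table 3 tolerances, and under them a 7-day repeat lies outside every window. This stands. A reader might infer that the Week 3, 5 and 7 repeats routinely overwrite the next scheduled value; the documents support that only if the analysis windows are contiguous.
- **The sequence number is undefined.** If it already ranks scheduled samples first, nothing is displaced. This also stands, and it makes the point conditional. It does not defend the rule, because the plan alone then does not show which value will be tabulated.
- **A spurious scheduled result is a different problem.** A reader might infer that the rule does harm by keeping a faulty draw over its redraw the next day. With date-ordered numbers the faulty draw is the scheduled sample, and a plain scheduled-first rule would keep it too. That is not displacement. It is a reason to require validity in the replacement rule.
- **Little rests on these tables.** Worst-grade counts, shift tables, adverse event tables and listings do not use the selected record. Escalation rests on safety review committee review and dose-limiting toxicities (Protocol 6.5.2), and all analyses are exploratory (SAP 3.2). This stands and keeps the point minor.

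It is also true that the rule is prespecified and does not look at the result. But access to a second sample depends on earlier abnormal results or safety concerns, so its effect need not be neutral.

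**Conclusion.** The point holds in conditional form and is minor. After baseline the SAP drops the scheduled-first priority that it applies at baseline, and the available text does not define the windows or the numbering that decide the consequence. Given collection-order numbering, displacement should be uncommon with ±3-day windows. With contiguous midpoint windows, an exact 7-day repeat would displace the next scheduled value for 3 or 4 of the 7 allowed visit days.

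The exposure is confined to Tables 3.3.1 and 3.3.4. The shift of about 3 to 33 ×10^9/L in a platelet visit mean is an illustration of sensitivity at 9 per dose, not an estimate; its direction is unknown. A reader might go further and infer that the primary safety conclusions are biased. The documents do not support that: laboratory results also enter through worst-grade counts, shift tables and listings, which this rule does not restrict. No sample size, power or error-rate figure changes.

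**What to change.** In SAP 8.3.2, replace the selection sentence for by-visit summaries with this order:

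1. Use the valid scheduled sample for that visit.
2. If it is missing or invalid, use the valid sample in the window closest to the nominal day, and the later one if two are equally close.
3. Use the sequence number only as a final tie-breaker.

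State the laboratory visit windows, including which window takes a midpoint day if they are contiguous, and say what the sequence number represents. Keep all unscheduled values in the worst-value and shift tables and in the listings.

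The cost is a few SAP sentences and minor programming. No visit, procedure or sample size changes.
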